### **4.4.2 Baseline and Change from Baseline**

Baseline is defined as the last non-missing measurement before or on randomization date. If more than one measurement was taken for a scheduled time point (i.e. blood pressure measurements and heart rate), the average value is used

Change from baseline will be displayed as the difference to baseline defined as:

$$\text{Change} = \text{Post baseline value} - \text{baseline value}.$$

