7.4 Dosage and administration

Patients will take two tablets once daily preferably in the morning with food. The starting dose will be 2.5 mg of vericiguat or matching placebo.

Titration steps at 2, 4 and 6 weeks include sham titration in placebo arm. Titration step at 6 weeks includes sham titration in 10 mg arm. The maximal dose of vericiguat is 10 mg o.d. in the 10 mg treatment arm, and 15 mg (5 mg + 10 mg tablet) o.d. in the 15 mg arm ([Table 7-3](#)). For justification of dose selection see [Section 3.2.1](#).

Table 7-3: Dosing plan

Dose step	Arm		
	Placebo	10 mg target dose	15 mg target dose
1	placebo	2.5 mg	2.5 mg
2	placebo	5 mg	5 mg
3	placebo	10 mg	10 mg
4	placebo	10 mg	15 mg

Titration will be based on systolic blood pressure (SBP) measurement, before intake of the study drug as follows:

- **Increase dose:** if SBP \geq 100 mmHg and SBP decrease is \leq 20 mmHg from previous visit, and not yet on highest dose
- **Maintain dose:** if SBP is between 90 mmHg and <100 mmHg, or SBP \geq 100 mmHg and SBP decrease is >20 mmHg from previous visit, or if already on highest dose step (after 3 uptitrations)
- **Decrease the dose:** if SBP <90 mmHg without symptoms of hypotension if on dose steps 2-4 (see [Table 7-3](#)) >2.5 mg, or temporarily interrupt if on 2.5 mg (starting dose or after down titration from a higher dose)
- **Interrupt the dose:** if SBP <90 mmHg with symptoms of hypotension

Dose decrease is possible at any time if the physician feels this is necessary for safety reasons.

The first dose of trial treatment will be administered at the trial site at the randomization visit. Subsequent dosing will be performed once daily preferably in the morning by the patient at approximately the same time each day. Patients will be instructed to take vericiguat with food.

Resumption of study drug after temporary interruption

Upon temporary interruption of the study drug due to intolerance, intake should be resumed as soon as medically justified at the discretion of the investigator. There is no defined maximum time limit for temporary treatment interruption. In all cases, the reason for study drug interruption or permanent study drug discontinuation must be recorded in the eCRF and in the patient's medical records. Titration rules following restart of study drug after temporary interruption of study drug are as follows:

- If restart before visit 5 (week 6): Restart at a scheduled visit and titrate according to the intervals in [Table 7-4](#).

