- f. 3 measurements, 2 min apart; measurements are taken prior to study drug intake. Additional measurement at 2h ± 15 min post study drug intake will be performed only at visit 2, and at visits 5-8 if dose is uptitrated from dose step 3 to step 4.
- g. Assessment of eligibility for PK/QT assessment.

Clinical Study Protocol
No. BAY 1021189 / 19334

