9.2.2 Visit 2 Baseline and Randomization – Day 1

Randomization occurs latest within 4 weeks after informed consent.

- Before randomization:
 - Assess patient eligibility (see Sections [6.1](#) and [6.2](#); for echo criteria see below)
 - KCCQ, EQ-5D-5L, PGIS (see Section [9.4](#))
 - Frailty assessment based on the Fried score
 - Assessment of NYHA class
 - Concomitant medications, record new or ongoing medication or changes in dosage (see Section [8.1](#))
 - Urine pregnancy test, if applicable.
 - Adverse events (see Section [9.6.1](#))
 - Only for patients participating in the optional accelerometry substudy: Activity tracking devices are planned to be collected (see accelerometry manual).
 - Physical examination including height and weight (BMI will be calculated automatically in the eCRF) (see Section [9.7.2](#))
 - Vital signs (BP and pulse rate), See Section [9.7.5](#).
 - 12-lead ECG to evaluate the eligibility of the patient for PK/QT assessment (see Section [9.7.4](#))
 - 6MWT
- Randomization to vericiguat once daily or placebo (see Section [7.3](#))
- Central lab blood samples for NT-proBNP, hematology, clinical chemistry, coagulation and biomarkers (see Section [9.7.1](#))
- Only to be collected for patients who signed the optional pharmacogenetics research informed consent: Central lab blood sample for pharmacogenetics (obtaining the informed consent for optional pharmacogenetics research and blood collection may also be performed at a later visit).
- Dispense study drug for the first 2 week interval until Visit 3 and instruct the patient on how to take the study drug
- Patient to take first dose of study drug (exact time of intake must be documented)
- Only in patients eligible for PK/QT assessment (all patients assessed as eligible based on the baseline ECG, see Section [9.7.4](#)) – ECG and PK sample should be collected time-matched, first ECG, subsequently PK sample:
 - 12-lead ECG (to be performed just before the PK sample is taken) 1-2h after study drug intake (exact collection times must be documented)
 - Blood sample for PK 1-2h after study drug intake (exact collection time must be documented)

- 2 h ± 15 min after study drug intake: Vital signs (BP and pulse rate) in sitting position after resting for at least 10 min, 3 measurements, 2 min apart. See Section [9.7.5](#).
- Schedule Visit 3 for Day 14±3

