### **Analysis time point and visit window**

Based on the randomization date, each scheduled visit date will be computed and a midpoint between two adjacent scheduled visit dates will be identified as the boundary of two visit windows. For example, Day 28 will be used to label the boundary between week 2 and week 6 windows. [Table 4-1](#) shows an example of the visit window for each analysis time point for KCCQ. Each visit date will be mapped to one visit window. For any particular window, if there are multiple measurements within the window then the one that is closest to the scheduled visit date will be used. In case there are multiple measurements on the same day, the latest one will be selected. Also note that the baseline is defined as the last non-missing measurement before first intake of study treatment ([Section 4.4.2](#)). In case KCCQ assessments may simultaneously be considered as baseline and follow up, for example if a patient takes first study treatment 14 days after randomization, under such scenario these measurements will be assigned as baseline only.

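### SAP 4.1 and 4.4.2 define baseline differently; 4.4.2 as written takes Day 1 post-dose blood pressure, pulse and (in PK/QT-eligible patients) ECG as baseline for exploratory safety outputs

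*SAP*

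**What the plan says.** SAP 4.4.2, the section named for the baseline rule, states: "Baseline is defined as the last non-missing measurement before or on randomization date". It sets no condition on dosing time.

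SAP 4.1, under the heading on analysis time points and visit windows, states that "the baseline is defined as the last non-missing measurement before first intake of study treatment" and gives 4.4.2 as its reference. It adds a KCCQ example: "if a patient takes first study treatment 14 days after randomization, under such scenario these measurements will be assigned as baseline only".

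Both are current text. SAP 7.1 records that Version 2.0 updated the definition of baseline, but does not say which wording prevails.

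The protocol fixes the Day 1 order of events:

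- Protocol 7.4: "The first dose of trial treatment will be administered at the trial site at the randomization visit".
- Protocol Table 9-1, footnote f: "Additional measurement at 2h ± 15 min post study drug intake will be performed only at visit 2" (and at Visits 5-8 after a particular uptitration).
- Protocol 9.2.2 (Visit 2): "2 h ± 15 min after study drug intake: Vital signs (BP and pulse rate) in sitting position".
- Protocol 9.2.2, PK/QT-eligible patients only: "12-lead ECG (to be performed just before the PK sample is taken) 1-2h after study drug intake".

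**The concern.** A cut-off by date and a cut-off by first intake agree only if nothing is measured between the first dose and the end of that day. Here something is. A baseline taken after the first dose absorbs any acute drug effect, and it does so only in the vericiguat arms. Later changes from baseline then understate the effect on blood pressure.

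The outputs exposed are:

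- the week-24 vital-sign comparisons and the listing of post-baseline systolic pressure below 90 mmHg (SAP 6.3.3.2);
- the ECG and QTcF changes (SAP 6.3.3.3);
- the by-arm baseline systolic pressure, diastolic pressure and heart rate (SAP 6.1.2).

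Protocol 3.3 names hypotension as the main risk of the drug, so the blood pressure summaries should rest on a clean pre-dose value.

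**Working it through.** **Step 1. Apply each rule to Visit 2 with the first dose on schedule.**

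| Measurement on Day 1 | SAP 4.1 (before first intake) | SAP 4.4.2 (on or before randomization date) |
|---|---|---|
| BP and pulse, all patients | pre-dose triplicate | triplicate 2 h after dose |
| ECG, PK/QT-eligible | pre-dose tracing | tracing 1-2 h after dose |
| ECG, not eligible | single pre-dose tracing | the same tracing |
| KCCQ, 6MWT | value before randomization | the same value |

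Protocol 9.2.2 places KCCQ and 6MWT before randomization and does not repeat them that day, so the last row is identical under both rules.

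**Step 2. Effect on the week-24 vital-sign comparison.** Let Y0 be the mean pre-dose value, equal across arms by randomization. Let p be the 2 h change unrelated to drug, d the placebo-corrected acute fall, and T the true week-24 difference, vericiguat minus placebo.

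- Post-dose baseline: placebo Y0 + p; vericiguat Y0 + p - d.
- Reported change: placebo Y24(placebo) - Y0 - p; vericiguat Y24(vericiguat) - Y0 - p + d.
- Reported difference: T + d. The drift p cancels.

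The documents give neither T nor d for this trial. For illustration only, with T assumed to be -3 mmHg:

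| assumed d (mmHg) | reported difference, T + d (mmHg) |
|---|---|
| 0 | -3 |
| 0.5 | -2.5 |
| 1 | -2 |
| 2 | -1 |

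The shift equals d whatever T is, and is nil when d = 0.

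**Step 3. QTcF.** SAP 6.3.3.3 plans a 90% CI for the mean change from baseline, summarized by visit and arm, and specifies no difference from placebo. If C is an arm's true mean change from the pre-dose tracing and q its whole change 1-2 h after the dose, the reported mean is C - q. This holds in the placebo arm too, because q includes any drift unrelated to drug. The supplementary SAP announced in SAP 2 may set its own QT baseline.

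**Step 4. Other outputs.** The baseline table would show post-dose pressures and heart rates. A first-dose systolic value below 90 mmHg would count as baseline and could leave the post-baseline listing. The by-visit count in the same section uses individual readings with no post-baseline restriction, so the value would still be counted there.

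**Step 5. Delayed first dose.** Take SAP 4.1's own example of a first dose 14 days after randomization. A Day 14 KCCQ is baseline under 4.1. Under 4.4.2 baseline stops at the randomization date, and the same questionnaire falls in the Week 2 window (Day 2 to Day 27, SAP Table 4-1). The primary variable for that patient then has two possible baselines. The number of such patients is not given.

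**The case against.** The strongest reply is that the intended rule is plain. SAP 4.1 states it. Protocol 9.2.2 lists vital signs and the eligibility ECG among the procedures before randomization. Table 9-1, footnote f, treats the 2 h set as additional to a pre-dose measurement. Protocol 9.7.4 calls the eligibility tracing the baseline ECG and lists it apart from the PK-matched ones. All of this stands, and harm requires someone to program 4.4.2 without regard to 4.1. But 4.4.2 is the section that carries the definition and the one 4.1 points to, so that is a realistic route to error.

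The acute effect may also be nil. The first dose is the 2.5 mg step, and Protocol 3.2.1 reports no blood pressure change at 10 mg against placebo in the earlier HFpEF trial. That stands as a limit on size.

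A reader might infer more than the documents support:

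- *Pre-dose and post-dose readings are pooled, halving the shift.* The averaging sentence, "If more than one measurement was taken for a scheduled time point (i.e. blood pressure measurements and heart rate), the average value is used", could suggest this. SAP 4.4.2.1 averages one set of three readings about 2 minutes apart, and the 2 h set is scheduled separately.
- *QTcF is biased like blood pressure.* Step 3 shows otherwise. The placebo-corrected QTcF analysis is in Protocol 10.6, and SAP 2 defers PK analyses to a supplementary plan not available here.
- *The vital-sign test loses a stated amount of power.* This would need T, d and an SD, none of which is given, for a test that SAP 6.3.3.2 calls explorative.
- *A safety signal is hidden.* SAP 6.3.1 dates treatment-emergent events from first application, not from baseline, and SAP 5.1 puts all patients' data in listings.
- *The primary analysis is contaminated.* With on-schedule dosing it is not. Protocol 7.4 puts the first dose at the randomization visit, so delayed dosing is an exception.

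**Conclusion.** The conflict is certain: two current sections of the SAP give different baselines, and the one bearing the title gives the wrong result if followed as written. The practical weight is small. Protocol 9.6 lists vital signs and ECG as exploratory safety variables, and the intended pre-dose rule can be recovered from the other passages.

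The supported size is a shift of d in the week-24 vital-sign difference, with d unknown and possibly zero, and a shift of the whole 1-2 h change in each arm's mean QTcF among PK/QT-eligible patients. Both rest on 4.4.2 being programmed literally; the QTcF part also rests on the supplementary SAP not setting another baseline. The only contact with the primary endpoint is the delayed-dose KCCQ case, which is probably rare. The change is minor but worth making because it is cheap.

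**What to change.** Put one rule in both SAP 4.1 and SAP 4.4.2, for example:

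> For vital signs, ECG and other safety variables, baseline is the last non-missing measurement before the first intake of study treatment (BP and heart rate: mean of the pre-dose triplicate). For patients never dosed, it is the last non-missing measurement on or before the randomization date. The Visit 2 post-dose vital signs and ECG are post-baseline.

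The never-dosed clause is needed because the FAS in SAP 5.1.1 contains all randomized patients, and a first-intake rule gives those never dosed no cut-off.

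For KCCQ and 6MWT when the first dose is delayed, the sponsor should reconcile the two sections to a single stated cut-off before unblinding.

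The cost is a few sentences and a dose-time check in the derivation. The times of first intake (Protocol 9.2.2), of each blood pressure reading (Protocol 9.7.5) and of the PK-matched ECGs (Table 9-1, footnote i) are already recorded. No new data are needed and the multiplicity scheme is untouched.

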#### **4.4.2.1 Vital Signs**

Three measurements of vital signs parameters will be taken at time intervals of about 2 minutes. Averages of non-missing values of these three measurements will be calculated and used for the statistical analysis. If only one of the planned measurements is available, this value will be used.

#### **4.4.3 Laboratory Data Handling**

Only the data provided by the central laboratory will be used for analysis, values from local laboratories will not be used.

For values which are below the lower limit of quantification (LLOQ), half the value of the LLOQ will be used for analysis. Differences between two values below the LLOQ will be assigned values of 0.

#### **4.4.4 Subgroup analyses**

The following subgroups will be considered for descriptive and exploratory analyses. To determine whether the treatment effect is consistent across various subgroups, the estimate of the between-group treatment effect (with a nominal 95% CI) for the primary endpoint will be estimated and plotted within each category of the following classification variables in all subjects:

- Gender: Male, Female
- Region:
  - Americas
  - Europe (incl. Israel and South Africa)
  - Asia/Pacific
- Heart rhythm: Atrial fibrillation (defined as atrial fibrillation or atrial flutter in baseline ECG), Sinus rhythm (defined as no atrial fibrillation and no atrial flutter in baseline ECG)
- Randomization time:
  - Before discharge from HF hospitalization
  - After discharge from HF hospitalization
  - Post IV diuretic treatment without hospitalization
- Time from qualifying event (HF hospitalization or IV diuretic) to randomization: <3 month,  $\geq$ 3 month
- Baseline Body Mass Index (BMI; kg/m^2):  $\leq$ 30,  $>$ 30
- Baseline Estimated Glomerular Filtration Rate (eGFR; mL/min/1.73m^2):  $\leq$ 60,  $>$ 60
- Diabetes: Yes, No

- COPD: Yes, No
- Anemia: Yes, No
- NYHA class: II, III
- Baseline KCCQ-PLS:  $<45$ ,  $45 - <75$ ,  $\geq75$
- Baseline subgroups defined by combined KCCQ-PLS and NYHA class criteria, as follows: KCCQ-PLS  $<65$  and NYHA II; KCCQ-PLS  $<65$  and NYHA III; KCCQ-PLS  $\geq65$  and NYHA II; KCCQ-PLS  $\geq65$  and NYHA III

## 5. Analysis Sets

### 5.1 Assignment of analysis sets

Final decisions regarding the assignment of patients to analysis sets will be made during the validity meeting (see Section 5.1.8).

Data from all patients who signed informed consent, regardless of their assignment to certain analysis sets, will be presented in individual subject data listings. In addition, the following analysis sets will be used for this study:

#### 5.1.1 Full analysis set (FAS)

All patients randomized will be valid for the FAS. The patients will be analyzed based on the planned treatment. The population characteristics (such as disposition, demographic and baseline characteristics etc.) will be based on FAS.

#### 5.1.2 FAS (KCCQ)

All patients randomized and treated (at least one dose of the study treatment), and have at least one observed KCCQ-PLS assessment at both baseline and post-baseline (excluding safety follow-up), will be valid for this analysis set. The primary analysis for the primary efficacy endpoint will be based on FAS (KCCQ).

#### 5.1.3 FAS (6MWT)

All patients randomized and treated (at least one dose of the study treatment), and who are able to perform at least one 6MWT assessment at both baseline and post-baseline (excluding safety follow-up), will be valid for this analysis set. The primary analysis for the secondary efficacy endpoint will be based on FAS (6MWT).

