9.2.7 Visit 7 – Day 84±3 (week 12)

Patients need to come for this visit without taking the morning dose of the study drug (this applies only for the study drug. All others medications shall be taken as scheduled)

- KCCQ, EQ-5D-5L, PGIC/S (see Section [9.4](#))
- Assessment of NYHA class
- Concomitant medications (see Section [8.1](#))
- Adverse events (see Section [9.6.1](#))
- Only for patients participating in the optional accelerometry substudy: Activity tracking devices are planned to be collected (see accelerometry manual).
- Physical examination
- Vital signs in sitting position (BP and pulse rate). See Section [9.7.5](#).
- 6 MWT
- Drug accountability, incl. exact time of last dose intake the day before, and collect unused study drug
- Optional uptitration/sham titration if not yet on target dose, dispense study drug in accordance with dosing regimen for the 6 week interval until Visit 8 and instruct the patient on how to take the study drug.
- Patient to take the study drug (exact time of intake must be documented)
- Only in case of uptitration from dose step 3 to dose step 4, 2 h ± 15 min after study drug intake: Vital signs (BP and pulse rate). See Section [9.7.5](#).
- Schedule Visit 8 for Day 126±3

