9.2.11 Premature discontinuation visit – at time of permanent discontinuation

This visit is applicable only for patients who prematurely discontinue the study drug intake (Either by decision of the investigator or by the patient.)

- KCCQ, EQ-5D-5L, PGIC/S (see Section 9.4)
- Frailty assessment based on the Fried score
- Assessment of NYHA class
- Concomitant medications (see Section 8.1)

- Adverse events (see Section 9.6.1)
- Physical examination incl. weight
- Vital signs (BP and pulse rate). See Section 9.7.5.
- 12-lead ECG (see Section 9.7.4)
- 6MWT
- Central lab blood sample for NT-proBNP, hematology, clinical chemistry, coagulation and biomarkers.
- Drug accountability, incl. exact time of last dose intake the day before, and collect unused study drug
- Schedule Visit 12 for 30±7 days after last dose

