where Y_{ijklm} is the change from baseline in PLS to visit j for patient i; μ is the intercept, β is the baseline covariate effect, x_i is the baseline PLS for patient i, t_k is the fixed effect of treatment k, r_l is the fixed effect of region l, h_m is the fixed effect of heart rhythm m (atrial fibrillation and sinus rhythm), v_j is the fixed effect of visit j, $(tv)_{jk}$ is the interaction effect of treatment k by visit j, s_i is the random effect of patient i and $\varepsilon_{ij} \sim \text{Normal}(0, \sigma^2)$ represents the residual variance component with $\text{corr}(\varepsilon_{ij}, \varepsilon_{ij'}) = \rho_{jj'}, j \neq j'$

Further, based on the anchor-based interim analysis (see Section 10.5), the percentages of responders with MCID, moderate, and large differences at each visit will be summarized and nominal p-values will also be provided. In addition, cumulative distribution function of change from baseline at 24 weeks for the KCCQ PLS domain will be plotted to compare the proportion of patients who are meeting certain threshold from vericiguat and placebo arms (see Section 10.5).

As a supportive analysis, the MMRM using the above model will be applied to all assessments post-baseline prior to study drug termination.

Additional sensitivity analyses will be performed. Analysis using data imputation approaches based on different missing data mechanisms will be investigated, including tipping point analysis. Details of such methods will be described in the SAP.

Secondary efficacy variable:

The secondary endpoint is change from baseline in the 6 MWT at 24 weeks.

The estimand of interest is the de facto or treatment policy estimand.

Population: Defined through appropriate inclusion/exclusion criteria (see Section 6.1 and Section 6.2) to reflect the targeted patient population and restricted to those who are able to perform the 6 MWT at baseline.

Variable: Change from baseline in 6 MWT from baseline to Week 24.

Measurement of intervention effect: Regardless of stopping study treatment or adherence to study treatment.

Summary measure: Difference of LS means at Week 24.

The secondary endpoint will be analyzed in the same manner as the primary endpoint. For those patients who are too sick to perform the test at any post baseline visit, a score of 0 will be assumed. further sensitivity analyses will be specified in SAP.

Other efficacy variables:

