### 6.2.4 Secondary efficacy variable

The secondary endpoint is change from baseline in the 6 MWT at 24 weeks. The estimand of interest is the de facto or treatment policy estimand.

Population: Defined through study inclusion/exclusion criteria (see protocol Section 6.1 and 6.2).

Variable: Change from baseline in 6 MWT from baseline to Week 24.

Approach of intervention effect: Regardless of stopping study treatment or adherence to study treatment.

Summary measure: Difference of LS means at Week 24.

[figure not shown]
The secondary endpoint will be analyzed in the same manner as the primary endpoint and on the KCCQ (6MWT) (Section 5.1.3). Missing data will be imputed based on a pattern-mixture model with control-based pattern imputation (Appendix 9.1). For those patients who had died during the study, a score of 0 will be assumed from the time of death onward.

A supportive analysis will be repeated using the MMRM model without any missing data imputations. Also, the same model will be applied to all assessments post-baseline prior to study treatment termination.

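### The SAP admits patients to the confirmatory 6MWT analysis only if they walked after baseline, and omits the protocol's zero score for patients too sick to walk, without declaring either change

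*SAP*

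**What the plan says.** Protocol 10.3.1 sets the 6MWT population by the eligibility criteria, "restricted to those who are able to perform the 6 MWT at baseline". It adds a scoring rule: "For those patients who are too sick to perform the test at any post baseline visit, a score of 0 will be assumed". The endpoint is otherwise analysed like the primary, under a treatment-policy estimand.

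SAP 6.2.4 keeps that estimand and states the population without any post-baseline condition: "Population: Defined through study inclusion/exclusion criteria". Its only zero rule is for death: "For those patients who had died during the study, a score of 0 will be assumed from the time of death onward". Other missing walks go to the control-based imputation of Appendix 9.1.

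SAP 5.1.3 defines the set actually analysed. Beyond randomisation and one dose, it takes only patients "who are able to perform at least one 6MWT assessment at both baseline and post-baseline (excluding safety follow-up".

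SAP 7.1.1 reports no changes from the protocol, and the version history in 7.1 mentions neither point. SAP 6.2.4 also calls the set KCCQ (6MWT), a name defined nowhere and apparently a slip for FAS (6MWT).

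**The concern.** The two documents give different answers for the same patients. Entry to the SAP set depends on something that happens after randomisation, namely surviving and being able to walk. That conflicts with a treatment-policy estimand in a population fixed at baseline. The patients lost are those with the worst outcomes, to whom the protocol assigns the lowest score.

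The test is part of the alpha-controlled family (protocol 10.3.1, SAP 6.2.5). Suppose one dose succeeds on the primary and then on its 6MWT. Its 0.025 is then re-used for the other dose's primary hypothesis, which can be tested at 0.05. An undeclared choice about who is in the 6MWT set can therefore reach a primary conclusion.

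**Working it through.** **When a patient can enter the set.** Protocol 9.2 schedules the first post-baseline 6MWT at Visit 7 (week 12) and the next at Visit 9 (week 24). An earlier test arises only at the premature-discontinuation visit: "This visit is applicable only for patients who prematurely discontinue the study drug intake". Tests at the safety follow-up visits do not count under SAP 5.1.3.

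**What each document does with the same patient.**

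| Patient (treated, baseline walk done) | Protocol 10.3.1 | SAP 5.1.3 and 6.2.4 |
|---|---|---|
| Too sick to walk at every post-baseline test visit | 0 | Not in the set |
| Walks at week 12, too sick at week 24 | 0 at week 24 | Imputed from the placebo model, given the patient's own earlier walks |
| Dies before any post-baseline walk | 0 (handled as for the primary) | Not in the set, so the death zero is never applied |
| Walks at week 12, then dies | 0 | 0 |

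They agree only in the last row. Neither supportive analysis in SAP 6.2.4 closes the gap. One is described as "A supportive analysis will be repeated using the MMRM model without any missing data imputations"; the other uses only on-treatment data.

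**Planned power, reproduced.** Inputs from protocol 10.4 and 10.3.1: 245 per arm, SD 80 m, two-sided alpha 0.025 per dose (critical value 2.241).

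- SE = 80 × √(2/245) = 7.23 m
- +30 m: 30/7.23 − 2.241 = 1.909, power 97.2% (stated 97%)
- +22.3 m: 22.3/7.23 − 2.241 = 0.844, power 80.1% (stated 80%)

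The protocol's arithmetic is sound. It makes no allowance for zeros.

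**Effect of an imbalance (illustration).** The documents give no baseline distance B. Assume B = 250-350 m and a mean change of 0 to +30 m in walkers. A patient scored 0 has change −B, so moving one percentage point of an arm (about 2.5 of 245 patients) from excluded to scored 0 shifts that arm's mean by 0.01 × (B + 0 to 30):

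- lowest: 0.01 × 250 = 2.5 m
- highest: 0.01 × (350 + 30) = 3.8 m

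With +30 m among walkers and a three-point imbalance, the zero-rule difference is 30(1 − f_v) − B(f_v − f_p), where f_v and f_p are the vericiguat and placebo fractions scored 0:

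- 5% vericiguat, 2% placebo: 28.5 − 0.03B = +21.0 m (B = 250) to +18.0 m (B = 350)
- 2% vericiguat, 5% placebo: 29.4 + 0.03B = +36.9 m to +39.9 m

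If these patients are excluded, the difference stays at +30 m in both cases.

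**Power cost of the zero rule (illustration).** With a fraction p of zeros in each arm, the difference is 30(1 − p). Each arm's variance is (1 − p)·80² + p·SD_b² + p(1 − p)(m + B)², where SD_b is the baseline SD (assumed 80-100 m) and m is the walkers' mean change (0 on placebo, 30 on drug).

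| Zeros per arm | SD of change | Power at the resulting difference |
|---|---|---|
| 1% | 84-89 m | 93-95% |
| 3% | 91-103 m | 82-90% |
| 5% | 97-116 m | 70-83% |

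**The same gap in FAS (KCCQ).** SAP 5.1.2 also requires a post-baseline value. The first KCCQ is at week 2, so fewer patients can be lost, and the only zero rule bypassed is the one for death.

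**The case against.** The strongest reply concerns the set itself. Protocol 10.2 bases all efficacy analyses on a FAS that requires an observed outcome measure. Because the outcome is a change from baseline, that could be read as a post-baseline value, making SAP 5.1.3 a mere implementation. The population lines describe the estimand rather than the analysis set, and SAP 6.2 allows exceptions through Section 5.1. This does not hold up. The protocol says neither post-baseline nor 6MWT, and that reading would cancel its own zero rule for anyone too sick at every visit. Permission inside the SAP does not make the set consistent with the protocol.

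A second reply is that the SAP is silent on the too-sick rule rather than repealing it. That is true, but a programmer following 6.2.4 and Appendix 9.1 would impute.

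A third is that few patients may be affected. Patients unable to do the test are excluded at entry, those who stop drug continue visits, and dropout is considered negligible. This stands as a caution on size, although the documents give no rate.

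The illustration also depends on its inputs. Patients who become too sick may start lower. Assuming 150-200 m, the shift is 1.5-2.3 m per point, and power with 5% zeros is about 88-91% (baseline SD 80 m). The formula ignores the model's baseline adjustment.

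Finally, the alpha route is gated. When only one primary succeeds, re-use needs success on the same dose's 6MWT, and it changes the outcome only if the other primary p-value lies between 0.025 and 0.05. That narrows the route but does not close it.

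**Conclusion.** The concern holds, and the conflict must be resolved. Following the SAP exactly gives a confirmatory 6MWT analysis that differs from the protocol's in both population and scoring, while the SAP states that nothing changed. This follows from the text and needs no assumption.

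The size and direction of any bias cannot be derived from the documents. The metre and power figures above are illustrations resting on an assumed baseline distance, an assumed spread and an assumed share of zeros. They show that a few percent of patients can matter against a 30 m planning effect, not that they will. The FAS (KCCQ) gap is the same in kind but smaller.

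**What to change.** 1. Define FAS (6MWT) and FAS (KCCQ) as randomised, treated patients with a baseline value of the measure.
2. Score deaths 0 from death onward, including deaths before the first post-baseline assessment. Impute other missing values by Appendix 9.1, whose sequence already starts from baseline.
3. Reconcile SAP 6.2.4 with protocol 10.3.1. Either restore the zero for patients too sick to walk, or declare and justify its removal in SAP 7.1.1 and keep the zero rule as a sensitivity analysis. Settle this before unblinding.
4. Correct the set name in SAP 6.2.4 to FAS (6MWT).

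The cost is SAP wording and programming. Restoring the zero requires the reason for a missed test. Protocol Appendix 16.1 requires only oxygen and walking-aid use to be recorded in the eCRF, so check first whether the reason is captured. The zeros also cost power, as shown above. Under a baseline-only set, a surviving patient with no post-baseline walk, and not scored 0 as too sick, is imputed from baseline and the placebo model alone; the SAP should say so.
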